9.3.6 Surgery

The following assessments are performed on the day of surgery:

- Fundus photography will be performed in the operating room during surgery. This will be post bleb placement and will record the position of the bleb relative to the retinal anatomy.
- Where available, the following assessments will be performed:
 - Surgery video-recording,
 - and/or intra-operative OCT.
- Vital signs 30 and 60 minutes after surgery
- Blood and where possible urine for PCR 60 minutes after surgery.
- Adverse events.
- Concomitant medications.

9.3.7 Follow-up Procedures

Patient follow-up visits are outlined in the study schedule in [Section 2](#).

9.3.7.1 Follow-up Day 1 Clinical and Laboratory/Diagnostic Measurements

- Vital signs
- Ophthalmological examination:
 - BCVA,
 - Slit-lamp examination,
 - Intraocular pressure (IOP),
 - Fundoscopy,
 - OCT including an infra-red imaging montage,
 - Fundus photography.

- Clinical laboratory samples (except coagulation and kidney function ([not unless clinically indicated in <18 years old])).
- Blood for PCR.
- Urine for PCR.
- Urinalysis (not unless clinically indicated in <18 years old).
- Adverse events.
- Concomitant medications.

9.3.7.2 *Follow-up Week 1, 2, 4, 12, 24 and 48 Clinical and Laboratory/Diagnostic Measurements*

- Vital signs.
- Physical examination (Week 48 only).
- Ophthalmological examination:
 - BCVA,
 - Contrast sensitivity (Weeks 12, 24, 36 and 48 only),
 - Slit-lamp examination,
 - Intraocular pressure (IOP),
 - Fundoscopy,
 - Autofluorescence (Weeks 4, 12, 24 and 48 only),
 - OCT including an infra-red imaging montage,
 - SKP, full-field GATE static perimetry and Microperimetry (Weeks 2, 4, 12, 24, 36 and 48 only),
 - Fundus photography (Weeks 2, 4, 24, 36 and 48 only),
 - Fundus photomontage (Week 48 only),
 - ERG (Weeks 24 and 48 only),
 - VFQ25 questionnaire (Week 48 only) / CVAQC (when possible, 48 week only).
- Clinical Laboratory Samples (except coagulation, at Weeks 4, 24 and 48 only, not in <18 years old unless clinically indicated).
- Urinalysis (Weeks 4, 24 and 48 only), (not unless clinically indicated in <18 years old).
- Pregnancy test (Weeks 4, 12, 24, 36 and 48 only), (not unless clinically indicated in <18 years old).
- Blood for PCR.
- Urine for PCR.
- Blood for Immunology (For all the patients at Weeks 4, 12, and 24 only). In patients with positive antibody response at Week 24, additional immunology blood testing will be performed at Week 36 and/or Week 48 to document the antibody response kinetic until the value returns to baseline in these patients (the need for sample collection beyond Week 48 (if needed) would be collected in the long term safety study).
- Adverse events.
- Concomitant medications.

9.3.8 Samples for PCR

Blood and Urine samples for PCR are required to be taken at screening and at follow-up visits post administration of SAR421869; 60 minutes after surgery, Day 1, Weeks 1, 2, 4, 12, 24, 36 and 48.

The processing of the blood samples for PCR analysis will be performed at the designated hospital by a person designated by the PI. The samples will be labelled with the patient number, date of collection and visit number. They will then be stored in the freezer at $\leq -70^{\circ}\text{C}$ prior to shipment to the Sponsor designated company. The shipment of samples will be on dry ice. The Sponsor clinical project manager or designee will be notified at least 24 hours in advance of any shipment.

Urine and blood samples will be analyzed using PCR to assess the presence of vector RNA and/or DNA.

9.3.9 Samples for Immunology

Samples for immunology are required to be taken at baseline (Day -1) and at the following follow-up visits post administration of SAR421869: Weeks 4, 12, and 24.

The processing of the blood samples for immunology analysis will be performed at the designated hospital by a person designated by the PI. The samples will be labelled with the patient number, date of collection and visit number. They will then be stored in the freezer at $\leq -70^{\circ}\text{C}$ prior to shipment to the Sponsor designated company. The shipment of samples will be on dry ice. The Sponsor clinical project manager or designee will be notified at least 24 hours in advance of any shipment.

Blood samples collected for immunology will be analyzed by the Sponsor designated company using Western blot analysis or ELISA.

9.3.10 Future Use of Samples

For subjects who have consented to it, the samples that are unused or left over after testing may be used for other research purposes (excluding genetic analysis) related to ophthalmology.

Your sample(s) will be transferred to a Sanofi site (or subcontractor site). Your sample(s) will be handled and stored at a secure site specialized for such investigations under the responsibility of the sponsor up to 15 years after completion of the final report of the main clinical. Thereafter, all samples will be destroyed.

9.3.11 Ophthalmological Assessments

Ophthalmological assessments will be carried out by certified individuals at the study site. As far as possible, for each patient, assessments will be performed by the same individual at each visit. Technical details of all ophthalmological assessments will be provided in the investigator site file. All findings will be documented in the source documentation and the appropriate CRF.

Studies have shown that a number of imaging modalities provide a sensitive method of monitoring disease progression and response in retinal dystrophies.

9.3.11.1 Best-Corrected Early Treatment Diabetic Retinopathy Study (ETDRS) Visual Acuity

A BCVA examination will be performed using the EVA (electronic visual acuity) testing system according to the recommended protocol. Early Treatment Diabetic Retinopathy Study (ETDRS) chart testing will be used as a back-up in case the EVA is not functioning or available. In such cases the same method used to record BCVA at the screening visit for a given patient should be used throughout the study.

9.3.11.2 Contrast sensitivity

A contrast sensitivity assessment will be performed using the Sloan Low Contrast Letter acuity chart. In low vision patients, functional vision, eg, the ability to recognize faces and read moderate size print and the orientation and mobility capacities were better correlated to contrast sensitivity levels than visual acuity measurements (23, 44). The 100%, 2.5%, and 1.25% contrast level Sloan Low Contrast Acuity charts will be used for testing. For detailed instructions see [Appendix D](#).

Contrast sensitivity is not to be measured using both eyes.

9.3.11.3 Slit-Lamp Examination

Slit-lamp examination will be performed using the investigator's standard procedure. This procedure will be the same for all subjects examined. Observations will be made to indicate the absence or presence of findings for ocular adnexa, anterior and posterior segments. Intraocular inflammation will be graded using a standard scale.

9.3.11.4 Fundoscopy

Dilated funduscopic examination will be performed according to the investigator's standard practice. Investigators will specifically document the presence or absence of retinal detachment, retinal tears or holes, subretinal hemorrhage, exudation, fluid or fibrosis. Additional observations will also be documented.

9.3.11.5 Intraocular Pressure Measurement

Applanation tonometry will be used for IOP measurements.

9.3.11.6 Optical Coherence Tomography

Optical coherence tomography (OCT) is a non-invasive technique that provides high resolution axial images of the retina. A low coherence infrared source is used to image the retina and a portion of coherent backscattered light is detected using an optical interferometer. Depth and intensity information can be captured digitally to visualize the structural morphology of the intraretinal layers. Spectral domain OCT (SD-OCT) is the most advanced method available and provides high resolution, rapid scanning, high repeatability and the capacity for transverse scans and the 3-dimentional mapping of single retinal layers. Macular thickness, subretinal fluid, and other architectural OCT features provide useful information on

the transverse and axial location of retinal lesions. Optical coherence tomography (OCT) will be performed using the Spectralis SD-OCT imaging system (Heidelberg Engineering) to evaluate the cross-sectional anatomy of the macula and document areas of retinal atrophy. The Spectralis system will also be used to collect infra-red images for the infrared imaging montage.

9.3.11.7 Fundus Photography

Fundus photography remains an invaluable tool to record the characteristics of the retina at any one stage of the disease and is used in combination with other imaging modalities (eg, auto fluorescence) to accurately map the appearance of the atrophy. A suitable fundus camera, (Zeiss FF4 series and the Topcon TRC-50EX or similar) will be used to document the retinal anatomy. At screening a seven field retinal photomontage will be taken to document the whole retina and standard photographs at subsequent visits (at the 35°setting to document the appearances of the macula and posterior pole) with specific emphasis on recording the treated area of the retina.

9.3.11.8 Electroretinogram

Full field electroretinography (ERG) measures the electrical responses of various cell types in the retina, including the photoreceptors, inner retinal cells bipolar and amacrine cells, and the ganglion cells. It is a non-invasive technique in which electrodes are placed on the cornea and the skin near the eye. During a recording, the patient's eyes are exposed to standardized stimuli and the resulting ERG signal is displayed showing the time course of the signal's amplitude. The ERG is composed of electrical potentials contributed by different cell types within the retina, and the stimulus conditions (flash or pattern stimulus, whether a background light is present, and the colors of the stimulus and background) can elicit stronger response from certain components.

If a dim flash ERG is performed on a dark-adapted eye (scotopic), the response is primarily from the rod system and flash ERGs performed on a light-adapted eye (photopic) will reflect the activity of the cone system. In response to sufficiently bright flashes, the ERG will contain an 'a-wave' (initial negative deflection) followed by a 'b wave' (positive deflection). The leading edge of the a-wave is produced by the photoreceptors, while the remainder of the wave is produced by a mixture of cells including photoreceptor inner segments, bipolar, amacrine, and Mueller cells.

A full field electroretinogram will be conducted using the standard procedure according to the ERG Standardization Committee of the International Society for Clinical Electrophysiology of Vision (ISCEV). Stimulus protocols for both scotopic and photopic function will be performed.

Multifocal electroretinography will be performed using the VERIS multifocal ERG according to the manufacturer's protocol.

9.3.11.9 Perimetry

Semi-automated Kinetic Perimetry (SKP) and Full-field German Adapative Thresholding Estimation (GATE) Static Perimetry are non- invasive, psychophysical tests that can rapidly and accurately assess the visual fields and create a detailed map of the retina documenting scotoma and the level of retinal function at specific regions. Compared to manual Goldmann kinetic perimetry, Semi-automated Kinetic Perimetry (SKP) allows greater standardization, control, and documentation of how the testing is performed, and minimizes the variability normally observed when different perimetrists test the same patient.

Full-field Static Perimetry assesses the sensitivity of the entire field of vision through estimation of thresholds at specific loci determined by the number of test locations and the pattern of the grid. The Swedish Interactive Thresholding Algorithm (SITA) fast strategy for static perimetry was initially optimized specifically for glaucoma, however, a new fast strategy, GATE, has been shown to be appropriate for retinal disease. Using the GATE strategy and radially-oriented, centrally condensed grids that extend from 56° nasally to 80° temporally, the entire full field is captured. The centrally condensed grid captures detail of sensitivity boundaries and gradients within the central portion of the field and, thus, can more precisely define remaining visual field in advanced disease. The differential luminance sensitivities are exported digitally for computation and modelling to create a “Hill of Vision”, from which volumetric estimates of retinal function can be measured for the entire Hill of Vision or any subregion therein.

Perimetry (both Semi-automated Kinetic Perimetry (SKP) and Full-field GATE Static perimetry) will be performed using the Haag Streit Octopus 900 perimeter.

Microperimetry will also be performed on the MP1. The MP1 provides a quantitative assessment of fixation by tracking fundus movements while the patient looks steadily at the fixation target. The MP1 can also accurately map a scotoma by delineating the absolute or relative non-seeing areas within the visual field. This is accomplished by projecting a light stimulus onto the patient’s retina until it becomes visible to the patient. With the MP1 it is possible to monitor the evolution of a disease and the exact changes it effects on a patient’s vision over the long term, because follow-up examinations are automatically performed in previously examined areas.

9.3.11.10 Autofluorescence Imaging

Autofluorescence imaging of the retina will be performed to document the distribution of lipofuscin and degenerative geography using the Spectralis system (Heidelberg Engineering). Fundus autofluorescence (FAF) is a non- invasive imaging technique to visualize lipofuscin, particularly in the parafoveal area. Abnormally increased FAF suggests RPE dysfunction, while decrease FAF indicates RPE atrophy and photoreceptor death (38). Images are acquired using a confocal laser ophthalmoscope system effectively gathering light from a single focal plane and eliminating AF from sources anterior to the retina (39).

9.3.11.11 Visual Function Questionnaire (VFQ-25)

An individual's own perception of vision-related quality of life is perhaps one of the most meaningful measures of that individual's visual function level. The National Eye Institute (NEI) Visual Functioning Questionnaire (VFQ-25) was developed to measure vision-specific health-related quality of life.

The VFQ-25 assesses difficulty with near vision activities, difficulty with distance vision activities, limitations in social functioning due to vision, role limitations due to vision, dependency on others due to vision, mental health symptoms due to vision, future expectations for vision, driving difficulties, pain and discomfort in or around the eyes, limitations with peripheral vision and color vision. The VFQ-25 questionnaire was developed from patient focus groups representing a diverse set of visual conditions, the intention being to develop a scale that can be generalized to all patients with vision deficits, regardless of cause. Across the range of developmental conditions (cataract, glaucoma, AMD, and diabetic retinopathy), as well as other conditions as diverse as corneal diseases and vascular occlusions of the retina, NEI-VFQ scores vary in the expected direction with differences in visual performance and disease state.

The Cardiff Visual Ability Questionnaire for Children (CVAQC) will be administered to children aged 6 to <18 years old. This PRO instrument measures the self-perceived visual ability in visually impaired children and young people aged 6 to 17 years. The 25-item Cardiff Visual Ability Questionnaire for Children (CVAQC) is a short, psychometrically robust and a selfreported instrument that works to form a unidimensional scale for the assessment of the visual ability in children and young people with a visual impairment. A list of 121 items was generated from 13 focus groups with children and young people with and without a visual impairment. A long 89-item questionnaire was piloted with 45 visually impaired children and young people using face-to-face interviews. Rasch analysis was used to analyze the response category function and to facilitate item removal ensuring a valid unidimensional scale. The validity and reliability of the short questionnaire were assessed on a group of 109 visually impaired children (58.7% boys; median age 13 years) using Rasch analysis and intraclass correlation coefficient (ICC). The final 25-item questionnaire has good validity and reliability as demonstrated by a person separation index of 2.28 and reliability coefficient of 0.84. The items are well targeted to the subjects with a mean difference of -0.40 logit between item and person means, and an ICC of 0.89 demonstrates good temporal stability ([45](#)).

9.3.12 Medication, Adverse Event and Concomitant Medication Review

Review of concomitant medication and adverse events will be conducted by a physician at all visits and be recorded in the electronic CRF and reported as required.

9.3.13 Post-surgical ophthalmological adverse events

Patients who develop post-surgical complications such as ocular inflammation and raised IOP should be treated according to local standard of care procedures.

Intraocular inflammation worsening during the course of treatment with the protocol defined anti-inflammatory regimen (see [Section 9.2.2](#) Intraocular Injection) or persisting or occurring after the completion of the protocol defined anti-inflammatory regimen must be recorded as a post-surgical ophthalmological adverse event.

In this setting the treatment and follow-up of the patient will be at the discretion of the investigator, guided by the severity and longevity of the inflammation, in an effort to minimize the risk of loss of visual function as a result of the ongoing inflammatory process. In the situation where the intraocular inflammation is clinically worsening the presence of an intraocular infection should be excluded.

Treatment with high dose, oral corticosteroids (1 mg/kg/day for patients ≥ 50 kg; 0.5 mg/kg/day for patients < 50 kg; maximum dose not to exceed 80 mg/day for children < 16 years) is recommended for any patient manifesting worsening intraocular inflammation (eg, $\geq 2+$ for anterior chamber cells, ≥ 2 vitreous haze and/or cells, the presence of vitreous snowballs or retinal vasculitis). In such cases, the oral corticosteroids should be continued until the ocular inflammation is resolved and then tapered as appropriate.

Raised IOP greater than 30 mmHg must be recorded as a post-surgical adverse event and may be treated with IOP lowering drops with the patient reviewed within a week. If the IOP remains greater than 25 mmHg another pressure lowering drop will be added and the patient reviewed again within a week. This sequence will be repeated until the IOP remains below 25 mmHg. For increases in IOP occurring while the patient is receiving topical steroids per the recommended protocol defined anti-inflammatory regimen, consideration may be given to reducing the frequency of the topical steroids if the intraocular inflammation is controlled.

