For each patient, the following protocol required anti-inflammatory regimen including antibiotics and corticosteroid medications must be administered to reduce the possibility of clinically significant intraocular inflammation after subretinal injection procedure.

- **Immediately following the completion of the subretinal injection procedure administer:**
 - **In Children:** one dose of intravenous methylprednisolone 1 mg/kg for patients ≥ 50 kg or 0.5 mg/kg for patients < 50 kg. Maximum corticosteroid dose not to exceed 80 mg for children < 16 years.
 - **In Adults:** one dose of intravenous methylprednisolone 1 mg/kg.
 - At the discretion of the surgeon, a subconjunctival injection of corticosteroids (eg, Dexamethasone 5 to 10 mg) and/or a subconjunctival injection of antibiotics may be given.
- **Starting (post-operative) Day 1 administer/initiate:**
 - **In Children:** oral prednisone 1 mg/kg/day for patients ≥ 50 kg or 0.5 mg/kg/day for patients < 50 kg daily for 5 days, then reduce dose to 0.5 mg/kg/day for patients ≥ 50 kg or 0.25 mg/kg/day for patients < 50 kg daily for 5 days, then reduce dose by 10 mg daily until the corticosteroid taper is complete. Maximum corticosteroid dose not to exceed 80 mg for children < 16 years.

- **In Adults:** oral prednisone 1 mg/kg/day for 5 days, then reduce dose to 0.5 mg/kg/day for 5 days, then reduce dose by 10 mg daily until the corticosteroid taper is complete.
- Topical broad-spectrum antibiotic (eg, ofloxacin, ciprofloxacin, moxifloxacin, trimethoprim-polymyxin B or similar) QID for 7-10 days.
- Topical prednisolone acetate 1% (or similar) 4 times a day (QID) for 7-10 days, then three times a day (TID) for 7-10 days, then two times a day (BID) for 7-10 days, then once daily (QD) for 7-10 days. (Note: The frequency of the topical corticosteroid drops and the timing for the start of the taper may be adjusted as needed in response to the patient's manifestation of post-operative inflammation with the goal of resolving the post-operative ocular inflammatory response within 28 days after the surgical procedure).
- A topical steroid ointment (eg, sterdex, tobradex or similar) may also be given at bedtime (qhs) for 7-10 days at the discretion of the surgeon.

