Intraocular inflammation worsening during the course of treatment with the protocol defined anti-inflammatory regimen (see [Section 9.3.12](#) Medication, Adverse Event and Concomitant Medication Review) or persisting or occurring after the completion of the above protocol defined anti-inflammatory regimen must be recorded as a post-surgical adverse event.

For the management of intraocular inflammation persisting or occurring after the completion of the above post-surgical anti-inflammatory regimen or worsening during the course of the regimen see [Section 9.3.12](#) Specific Procedures - Medication, Adverse Event and Concomitant Medication Review

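### For an adult under 50 kg, the oral steroid dose recommended in 9.3.13 for worsening inflammation is half the prophylactic dose that 9.2.2 requires on Days 1–5

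*Protocol*

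**What the plan says.** Protocol 9.2.2 (Intraocular Injection) sets a mandatory post-operative regimen: "For each patient, the following protocol required anti-inflammatory regimen including antibiotics and corticosteroid medications must be administered". After intravenous methylprednisolone at the end of surgery, oral treatment starts on post-operative Day 1.

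- Adults, with no weight band: "oral prednisone 1 mg/kg/day for 5 days, then reduce dose to 0.5 mg/kg/day for 5 days", then down by 10 mg a day.
- Children, split at 50 kg: "oral prednisone 1 mg/kg/day for patients ≥ 50 kg or 0.5 mg/kg/day for patients < 50 kg daily for 5 days", then half of that for 5 days, then down by 10 mg a day.

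The same section allows the topical steroid to be adapted to post-operative inflammation at any weight: "The frequency of the topical corticosteroid drops and the timing for the start of the taper may be adjusted as needed".

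Protocol 9.3.13 (Post-surgical ophthalmological adverse events) covers inflammation that worsens during this regimen, as well as inflammation that persists or appears after it. It recommends high-dose oral corticosteroids at 1 mg/kg/day from 50 kg upwards and, below that, "0.5 mg/kg/day for patients < 50 kg; maximum dose not to exceed 80 mg/day for children < 16 years) is recommended for any patient" with worsening inflammation. The age limit in that text belongs to the 80 mg cap and not to the weight band. The section also says that "the treatment and follow-up of the patient will be at the discretion of the investigator", and "In such cases, the oral corticosteroids should be continued until the ocular inflammation is resolved and then tapered as appropriate".

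For the management of inflammation that outlasts or follows the regimen, "or worsening during the course of the regimen", 9.2.2 sends the reader to 9.3.12. That section deals only with reviewing and recording medication and adverse events. The management text is in 9.3.13.

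**The concern.** A dose written for worsening inflammation should not be below the dose the patient is already required to take. For one group, adults under 50 kg in the first five days, it is. Both rules can apply to the same patient on the same day, and no sentence states which dose prevails.

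The subject is safety-critical. The rationale for the current amendment says that glucocorticoid prophylaxis became mandatory after two serious uveitis cases following lentiviral vector injection, one of them in this study. Severe or persistent ocular inflammation is a named dose-limiting toxicity (8.5), and inflammation without signs of resolution at 28 days is a stopping criterion (8.4). These sections show why the dose text needs to be right. They do not show that harm followed from it.

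**Working it through.** **Inputs.** Doses are from 9.2.2 and 9.3.13. Visit windows are from Section 2 and 9.4. Patient numbers are from the Synopsis and Section 7. Body weights are assumed: 45 kg as the example, 40 to 49 kg as the range. The entry criteria in 8.2 set no minimum weight, so such adults can be enrolled.

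**Ratio = 9.3.13 dose ÷ 9.2.2 dose (mg/kg/day).**

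| Group | Days 1–5 | Days 6–10 |
|---|---|---|
| Adult, 50 kg or more | 1 ÷ 1 = 1.0 | 1 ÷ 0.5 = 2.0 |
| Adult, under 50 kg | 0.5 ÷ 1 = **0.5** | 0.5 ÷ 0.5 = 1.0 |
| Child, 50 kg or more | 1 ÷ 1 = 1.0 | 1 ÷ 0.5 = 2.0 |
| Child, under 50 kg | 0.5 ÷ 0.5 = 1.0 | 0.5 ÷ 0.25 = 2.0 |

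Only adults under 50 kg have a ratio below 1, and only on Days 1–5. The pattern suggests that the children's weight band was used in 9.3.13 without a separate adult line. The documents give no reason for a lower adult dose.

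**In milligrams, 45 kg adult.**

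- Days 1–5: 9.2.2 gives 45 mg/day and 9.3.13 gives 22.5 mg/day, a difference of 22.5 mg/day. At 40 kg it is 40 − 20 = 20 mg/day; at 49 kg it is 49 − 24.5 = 24.5 mg/day.
- Days 6–10: 22.5 mg/day under both.
- From Day 11, if inflammation has not resolved, 9.3.13 holds 22.5 mg while 9.2.2 tapers to 12.5, 2.5 and 0 mg. So 9.3.13 is higher by 10 mg on Day 11, 20 mg on Day 12 and 22.5 mg from Day 13.

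**Total shortfall to Day 5 if a site replaced the 9.2.2 dose with the 9.3.13 dose (45 kg).** From Day 1: 5 × 22.5 = 112.5 mg. From Day 2: 4 × 22.5 = 90 mg. From Day 4: 2 × 22.5 = 45 mg. From Day 5: 22.5 mg.

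**When it could arise.** Two scheduled visits can fall in the window. One is Day 1, which includes slit-lamp examination and fundoscopy and comes after the intravenous dose that opens the regimen. The other is a Week 1 visit held early: nominal Day 7 ± 3 gives Days 4–10, which overlaps the window on Days 4 and 5. Unscheduled visits on Days 2–5 could also fall there.

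**How many.** Part A may total 15 to 24 adults; less the 9 in Cohorts 1, 2 and 3a, that leaves 6 to 15. Cohort 4 adds up to 6, so 6 to 21 further adults, before any of the up to three replacement patients. Neither the share under 50 kg nor the share who worsen on Days 1–5 is given, so no number affected can be derived.

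**The case against.** The strongest reply is that the text already ranks the two rules. Section 9.2.2 is mandatory for each patient, and 15.8 says that all protocol items are to be followed exactly. Section 9.3.13 only recommends, leaves treatment to the investigator, opens with local standard of care and aims to limit loss of vision. Nothing in it suspends the required prednisone. On the ordinary reading 1 mg/kg/day remains the adult dose on Days 1–5, and cutting it would be a departure from 9.2.2. Nor does the text say whether the 9.3.13 dose replaces the prophylactic dose or is added to it. If added, a 45 kg adult would take 45 + 22.5 = 67.5 mg/day and there would be no shortfall.

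This stands as a limit on the consequence. A reader might infer that the protocol tells sites to halve the steroid when inflammation worsens, or that light adults were under-treated. The documents support neither. The milligram totals hold only if a site makes the replacement. The table shell in the 2019 memorandum attached to the SAP shows N=9, in Cohorts 1 to 3, and the amendment rationale describes the three Cohort 3 patients as already dosed. So few or none of the later adults may have been treated.

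The reply does not remove the conflict. The only oral dose that the protocol offers for worsening inflammation is, for this group, below the required one, and a site has to work out the ranking for itself. Nor is 9.3.13 lax overall: continuing oral steroids until resolution prevents the Day 11 taper and is protective.

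**Conclusion.** The point holds in a narrow form and should be fixed. For an adult under 50 kg whose inflammation worsens on Days 1–5, the dose recommended in 9.3.13 is half the dose required by 9.2.2: 22.5 against 45 mg/day at an assumed 45 kg. The inversion ends at Day 6. The ratio follows directly from the text and needs no assumption. The milligram figures rest on the assumed weights, and any actual shortfall rests on a site substituting the recommended dose for the mandatory one, which it need not do. The number of adults affected is unknown, probably small and possibly none.

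**What to change.** In 9.3.13, limit the under-50 kg band to children, as 9.2.2 does, so that the adult oral dose for worsening inflammation is 1 mg/kg/day at any weight. The sponsor and the DSMB should confirm that this is the intended dose.

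At a minimum, state that the 9.3.13 dose must not be lower than the patient's current 9.2.2 dose. The two options are not equivalent. The minimum wording removes the inversion on Days 1–5 but leaves an adult under 50 kg at 0.5 mg/kg/day on Days 6–10 (22.5 mg/day at 45 kg, against 45 mg/day under the first option), when the recommendation doubles the prophylactic dose for every other group.

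As an editorial correction, change the two pointers in 9.2.2 from 9.3.12 to 9.3.13.

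The cost is protocol wording, through the amendment procedure in 15.8, and a letter to sites. It needs no extra visits, staff or patients.
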